## 5.0 Study Visits

---

Subjects will be required to wear a mask. If they do not have one, a mask will be provided to them by the study staff.

Visit 1: This visit will take place at the UAMS RIOA. At this visit, informed consent discussion will be held. This visit is expected to take less than one hour. If a subject consents, their height and weight will be measured to determine their BMI. Questions will be asked about their medical history and medication use. Eligible, enrolled subjects will be shown a menu of the foods they will be asked to eat to elicit any food allergies or intolerances. If the subject is fasted for 8 hours, has not had caffeine in 12 hours, and has not strenuously exercised in 24 hours, they will undergo body composition testing and DXA scan. If these criteria cannot be met during this visit, subjects will perform these two tests at Visit 2. A blood sample will be drawn for Complete Blood Count (Labcorp). Randomization will occur. Future study visits are scheduled.

[figure not shown]
Visit 2: This visit will occur in a fasted state if the subject did not meet the body composition testing criteria at visit 1. Subjects will undergo body composition testing and DXA scan. Study meals eaten during the 2-day run-in phase will be dispensed. A

10mg dose of 3MH will be provided with instructions to mix it with water, ingest it at 1900, and record the time on the evening prior to study visit 3. Subjects are instructed to eat all of the provided food and add nothing but non-caloric seasonings and condiments. They may have their usual beverages but must not ingest any protein or amino acid supplements during this time. This visit will take place at the UAMS RIOA.

Visit 3: This visit will take place at the UAMS RIOA on the morning after subject completes the 2-day run-in meals. At this visit, subjects will report having fasted for 10 or more hours. This visit is expected to take about 13 hours. During this visit, subjects will be asked to provide blood/urine/saliva samples. They will ingest deuterated water (~3mL per kg body weight) at specific times (total dose divided into 10 aliquots and ingested every hour up to study hour 9:00) and 2g of a stable isotope of alanine (15N-alanine) dissolved in water. Two (group-specific) study meals will be served, one in the morning and one in the afternoon/evening. See **Figure 2** for a timeline. After the second saliva sample has been collected, subjects will go home and return to the study site the following morning having fasted overnight.

Visit 4: This visit will take place at the UAMS RIOA on the morning after visit 3. Subjects will fast overnight between visits 3 and 4. Approximately 24-hours after isotope ingestion, the final biological samples will be collected and the subject offered a snack and beverage. They will then be dismissed.

**Figure 2:**

---

## 6.0 Blinding

---

The study is a single-blind, randomized, controlled trial (RCT). While participants cannot be completely blinded as to the amount of protein in their meals, key investigators and outcomes assessors will be blinded to treatment assignment, making this a single-blind RCT from the investigators' perspective.

---

## 7.0 Randomization

---

Subjects will be randomized equally to one of three groups after they are determined to be eligible using a generated list of group designations that corresponds to subject ID. Efforts will be made to balance the sexes within each group. The three groups utilized are:

- 1) recommended dietary allowance for protein (RDA; 0.8g/kg/day);
- 2) habitual protein intake consistent with population level norms (NHANES; 1.1g/kg/day);
- 3) optimal protein intake (OPI; 1.5g/kg/day).

---

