#### **4.2 Exclusion Criteria**

1. Subject who does not/will not eat animal protein sources.

2. Body mass index >35.
3. Complete blood count lab results that indicate anemia or abnormal white blood cell counts.
4. History of chemotherapy or radiation therapy for cancer in the 6 months prior to enrollment.
5. Use of insulin to control blood sugar level.
6. Currently receiving androgen (e.g., testosterone) or anabolic (e.g., GH, IGF-I) therapy.
7. Currently using prescription blood thinning medications.
8. Unable or unwilling to suspend aspirin use for 7 days prior to Visit 3.
9. Unwilling to avoid using protein or amino-acid supplements during participation.
10. Subjects who are unwilling to fast overnight.

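### Allocation comes from an ID-keyed list with undefined efforts at sex balance and no stated concealment, and Visit 1 places randomization directly after the blood draw whose result decides eligibility

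*Combined protocol and SAP*

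**What the plan says.** Section 7.0 gives the order and the method. On order: "Subjects will be randomized equally to one of three groups after they are determined to be eligible". On method, assignment is made "using a generated list of group designations that corresponds to subject ID". On sex: "Efforts will be made to balance the sexes within each group". It does not say who generates or holds the list, when or in what order IDs are issued, whether strata or blocks are used, or how an assignment is released.

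The Study Schema, the Study Calendar and 5.0 all place consent and randomization at Visit 1. In 5.0 that visit also includes medical history, height and weight, a menu review and the blood draw, and "This visit is expected to take less than one hour". The sequence at its end reads: "A blood sample will be drawn for Complete Blood Count (Labcorp). Randomization will occur".

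Exclusion criterion 3 in 4.2 is "Complete blood count lab results that indicate anemia or abnormal white blood cell counts". Section 11.2 confirms that the Visit 1 sample is taken to decide eligibility.

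Section 6.0 says that "participants cannot be completely blinded as to the amount of protein in their meals, key investigators and outcomes assessors will be blinded to treatment assignment". Staff who consent, screen or randomize are not mentioned. Section 10.4 gives study staff access to the key that links codes to subjects.

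**The concern.** Randomization protects against selection only if the person deciding whether to enrol a candidate cannot tell which diet comes next. A list keyed to ID gives that protection when it is hidden from enrolling staff. It gives none when IDs run in order and the list is open. The plan does not say which applies. Undefined efforts at sex balance add a second opening, because nothing limits who makes them or whether they may alter an assignment.

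Three features give this some weight here:

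- Several exclusions in 4.2 are settled in conversation: eating animal protein, fasting overnight, avoiding supplements.
- Section 4.0 allows up to 50 enrolled for 30 completers, which leaves room to defer or re-order candidates.
- The tracer measurements follow a run-in matched to the assigned group (1.0, 4.5, 5.0), and the only biopsy is at Visit 4 (8.4). No pre-diet kinetic value exists to reveal or correct a selected difference between groups.

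A related problem is one of order. If randomization follows the blood draw within a visit of under an hour, a diet can be assigned while exclusion 3 is still open. Subjects removed afterwards would be removed with their group already assigned.

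**Working it through.** The plan gives no figure for allocation, so there is nothing of its own to reproduce. The power statement in 10.5 does not bear on this point. The check is a reading of the sections together, followed by an illustration of size.

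**Reading the sections together**

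1. Order. Section 7.0 puts eligibility before randomization. Section 5.0 puts randomization directly after the blood draw and describes no wait for the external laboratory's result. Sections 4.2 and 11.2 make that result part of eligibility. The sections agree only if the result is back within Visit 1 or if randomization in fact happens later; the plan says neither.
2. Concealment. Being randomized after eligibility fixes when the assignment is made. It does not say whether the next entry can be seen while eligibility is being judged. No other section supplies this.
3. Blinding. Section 6.0 covers key investigators and outcomes assessors. Who consents and screens is not stated, so 6.0 neither establishes nor rules out that those people are blinded.
4. Sex balance. The wording fits a list built separately for men and women, which needs nobody at enrolment to see assignments. It also fits case-by-case adjustment, which does. The text does not choose.

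**Illustration of size (assumptions not in the documents)**

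Inputs from the plan: 3 groups, 10 per group (10.5), one-way ANOVA at 0.05 (10.1). Assumed: no true diet effect, and selection that shifts the group outcome means by multiples of e, in SD units.

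Under the noncentral F distribution with 2 and 27 degrees of freedom, critical value 3.354, the noncentrality is λ = 10 × Σ(mᵢ − m̄)².

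- Pattern A, shifts −e, 0, +e: λ = 10 × 2e² = 20e².
- Pattern B, shifts +e, 0, +e (both outer groups move the same way): the mean is 2e/3, so λ = 10 × (e²/9 + 4e²/9 + e²/9) = 6.67e².

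| e (SD) | λ, A | False positives, A | λ, B | False positives, B |
|---|---|---|---|---|
| 0.3 | 1.80 | 18.9% | 0.60 | 9.3% |
| 0.5 | 5.00 | 45.8% | 1.67 | 17.8% |

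The table treats e as a shift in the outcome itself. If e is instead a shift in a trait that explains 25% of outcome variance (correlation 0.5), the outcome shift is e/2. Pattern A then gives λ = 20 × (e/2)² = 5e², and false-positive rates of 8.2% at e = 0.3 and 14.3% at e = 0.5.

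**The case against.** The strongest reply is that this is silence, not a defect. Section 7.0 states eligibility first. Foreknowledge would need IDs issued in order and a list open to those who screen, with no separate holder; none of this is stated. A list pre-stratified by sex would meet the balance sentence with nobody seeing an assignment. Blinding of key investigators may be a partial safeguard. DXA, body composition, height and weight are measured before the run-in meals, so some imbalance would show.

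Much of this stands. A reader might infer that the next diet is in fact known before enrolment, or that sex balance can be achieved only by someone watching the allocations. The documents support neither. A reader might also take the largest percentage in the table as the expected error. It belongs to a 0.5 SD shift in opposite directions in the outer groups. If steering kept small eaters out of the 1.5 g/kg/d group and frail subjects out of the 0.8 group, and each raised its group's mean, pattern B would apply instead. Rates for guessing the next diet, such as 46% for a list fixed at 10 per group or 61% for blocks of 3, also rest on list structures that the plan does not describe.

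What does not stand is that the eligibility-first clause settles the matter. It hides nothing, and 5.0 strains the order it sets. Baseline body measurements do not replace a pre-diet kinetic value.

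**Conclusion.** The point holds in limited form. Section 7.0 states a method, an ID-keyed list plus undefined efforts at sex balance, and nothing in the plan prevents the next diet from being foreseen or an assignment from being steered. Neither is shown to happen, and a safeguard may exist outside these documents. Separately, the order in 5.0 does not fit the eligibility-first rule in 7.0, because the blood count result is an exclusion criterion; the two must be reconciled.

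The size cannot be derived from the plan. Under the stated assumptions, a 0.3 SD outcome shift would raise a nominal 5% error to about 9% to 19% depending on its pattern, and to less if the steered trait is only partly correlated with the outcome. These figures show why 10 per group is sensitive to selection; they are not an estimate of bias. This should be corrected because a better-specified method is available at little cost.

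**What to change.** In 7.0, replace the ID-keyed list and the discretionary balancing with a computer-generated 1:1:1 sequence, stratified by sex, in permuted blocks of randomly varying size.

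- Name a holder who neither consents nor screens. The sequence could be loaded in REDCap, which 10.3 gives as an example database.
- Release one assignment at a time, only after every eligibility criterion, including the blood count result, is recorded for that subject.
- State that enrolling staff cannot see the sequence and that no assignment changes after release.
- Align the timing of randomization in the Study Schema, the Study Calendar and 5.0 with this rule.

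The cost is a protocol amendment touching those sections and a small one-time set-up. Group sizes may differ by one or two. Randomization may fall after Visit 1, but must still come before the group-matched run-in meals are prepared. No extra subjects or procedures are needed. If a concealed process is already in use, most of the change is writing it down.

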## 8.0 Biological Samples

---

Samples will be handled exclusively by study staff. All samples will be identified using the subject's unique study code; the key to which is kept on a secure UAMS server

(\\rscoa\\nmel\\[name]\\262424 2Meal study 2021 folder). All specimens will be stored in appropriate freezers in the PI's lab on the 7th floor of the UAMS Reynolds Institute on Aging (a secured access floor). All specimens will be discarded into biohazard receptacles within 7 years after conclusion of the study. With explicit written permission (on the ICF), muscle samples will be retained indefinitely for use in the PI's lab for future non-commercial uses that have been explicitly permitted by the UAMS IRB. The key to subject identity-study code will be deleted within 7 years of the conclusion of the study (e.g. closure of the study in Clara), regardless of whether any samples will be kept for future use.

### **8.1 Blood**

Blood samples (~5mL each) will be collected via venipuncture at the specific times mentioned in Figure 2 below (+/- 10 minutes). The blood will be placed into an EDTA (purple top) vacutainer tube, gently agitated 6 times, and placed onto wet ice until it is processed in a refrigerated centrifuge. Plasma will be pipetted into a labelled cryo vial for each specific time point and frozen at < -60 degrees C in the PI's lab. Two samples will be drawn (~10 mL) during Visits 3-4 (1 each).

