**1.0 Protocol Summary**

This will be a randomized study to demonstrate how animal-based protein-rich food sources can be used by older adults to increase protein intake within pre-existing dietary patterns. In this regard, we propose to augment the current dietary pattern of older Americans by readily available quality protein sources. To this end, we will investigate the effects of recommended and common protein intakes on the maintenance of whole-body protein balance and potential for muscle protein anabolism. Plans to accomplish project goal(s): We will study 3 groups of 10 older subjects during daily protein intakes of 0.8 (recommended dietary allowance [RDA]), 1.1 (National Health and Nutrition Examination Survey [NHANES]), and 1.5 (optimal [OPI]) g/kg/d. Due to common eating patterns in older adults (1), these protein intakes will be structured within 2 meals per day. A 2-day dietary lead-in (matching the subject's intervention paradigm) will proceed each dietary intervention. Whole-body protein balance will be determined during metabolic study days by oral ingestion of 2 grams of the stable isotope N-alanine, and a 24-hr integrated value of muscle protein synthesis will be determined by ingestion of deuterated water. Oral ingestion of 10mg of 3-Methyl-d3-L-histidine and analysis of urine samples will permit measurement of muscle protein breakdown during this period. Integrated post-meal blood EAA will also be determined, as we have demonstrated a relationship between peripheral EAA response and protein anabolism.

Study duration per subject will be about 2 weeks.

---

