### **10.1 Statistical Analysis**

Means by which experimental data will be analyzed or interpreted: Changes in whole-body protein synthesis, breakdown, flux, net balance, muscle protein synthesis, and plasma EAA area under the curve (AUC) between groups will be assessed with a one-way analysis of variance (ANOVA). In the event of a main effect of group, appropriate post-hoc comparisons will be carried out. Statistical significance will be accepted at an alpha level of  $p \leq 0.05$ .

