### **11.2 Blood Sampling**

Up to 10 mL of venous blood will be drawn during visits 3 and 4 in total. This is less than a tablespoon. The risks of drawing blood include pain, bruising, bleeding, and small chance of infection from the needle sticks. One ~5mL sample will be drawn during visit 1 to determine eligibility.

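### The plan promises an integrated post-meal EAA response and tests an EAA AUC, but its blood sampling text allows two draws, at most one of them after a meal

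*Combined protocol and SAP*

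**What the plan says.** - Section 1.0 sets out the outcome and its rationale: "Integrated post-meal blood EAA will also be determined, as we have demonstrated a relationship between peripheral EAA response and protein anabolism".
- Section 10.1 tests it as one of six listed outcomes: "plasma EAA area under the curve (AUC) between groups will be assessed with a one-way analysis of variance".
- Section 8.1 describes samples of about 5 mL each, taken "at the specific times mentioned in Figure 2 below (+/- 10 minutes"), and then gives the count: "Two samples will be drawn (~10 mL) during Visits 3-4 (1 each").
- Section 11.2, the blood risk text, says: "Up to 10 mL of venous blood will be drawn during visits 3 and 4 in total". The only other draw in the text serves a different purpose: "One ~5mL sample will be drawn during visit 1 to determine eligibility".
- Section 5.0 fixes the fed or fasted state. For Visit 3: "At this visit, subjects will report having fasted for 10 or more hours". Also for Visit 3: "Two (group-specific) study meals will be served, one in the morning and one in the afternoon/evening". Participants then fast overnight before Visit 4.
- Section 9.1 describes the assay, which gives plasma EAA concentrations.

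**The concern.** An integrated post-meal response needs enough samples after each meal to trace the rise and fall in concentration. The sampling text gives one sample at the visit where the meals are eaten and one the next morning after an overnight fast. If that is what happens, one of the six outcomes in section 10.1 would be reported as an integrated EAA response although it rests on two concentrations, at most one of them post-meal. EAA is also the mechanism that sections 1.0 and 2.1 offer for the anabolic effect, so readers would probably give a group difference in this AUC some explanatory weight.

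The damage is limited. The hypothesis in section 3.0 names only muscle protein synthesis and whole-body protein balance. Those come from deuterated water, saliva, muscle and urine, and do not use these plasma samples.

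**Working it through.** **Count and volume.** Inputs: about 5 mL per sample and two samples (8.1); at most 10 mL over Visits 3 and 4 (11.2).

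- 2 × 5 mL = 10 mL, which reproduces the volume in 8.1 and equals the ceiling in 11.2.
- 10 mL / 5 mL = 2 samples. Smaller draws could fit more samples under the ceiling, so the binding statement is the count in 8.1.

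**How many samples are post-meal.** Inputs from section 5.0.

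| Sample | State | Post-meal? |
|---|---|---|
| Visit 1 | Eligibility blood count, not EAA | Not applicable |
| Visit 3 (one) | Arrives fasted; both meals eaten during the visit | No if drawn on arrival; yes if drawn after a meal |
| Visit 4 (one) | After overnight fast | No |

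That leaves 0 or 1 post-meal values to describe 2 meals.

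**What a two-point area measures.** Let C1 be the Visit 3 concentration, C2 the Visit 4 concentration and T the interval between them, assumed equal for all participants. By the trapezoid rule:

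- total area = T(C1 + C2)/2, the mean of the two values times a constant;
- net area above the first sample = T(C2 − C1)/2, their difference times a constant.

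An ANOVA on either area is therefore an ANOVA on a mean or a difference of two concentrations. Section 10.1 does not say which area is meant. If C1 is post-meal, a one-unit rise in C1 raises the total area by T/2 and lowers the net area by T/2.

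As an illustration with assumed concentrations in arbitrary units, take C2 = 900 in every group:

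| Group | C1 | Total/T = (C1 + 900)/2 | Net/T = (900 − C1)/2 |
|---|---|---|---|
| RDA | 1200 | 1050 | −150 |
| NHANES | 1350 | 1125 | −225 |
| OPI | 1500 | 1200 | −300 |

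The total rises across the groups and the net area falls.

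**Dependence on draw time.** This is a second illustration, with an assumed curve. It has two identical EAA rises starting at 0.5 h and 8 h, each peaking 1.5 h later, and the final fasted sample is at 24 h. The true incremental area is taken above the fasting level over the whole 24 h. The two-point version averages the two excesses over that level and multiplies by the hours between draws.

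With a peak rise of 100% of the fasting level, the true area is 8.15:

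| Visit 3 draw | Two-point area | Share of true area |
|---|---|---|
| 0 h | 0.008 | about 0.1% |
| 2 h | 11.008 | 135% |
| 4 h | 6.157 | 76% |
| 7 h | 1.320 | 16% |
| 10 h | 6.906 | 85% |
| 12 h | 3.085 | 38% |

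The shares were the same for assumed peak rises of 20% and 50%. On this curve the two-point area is governed by when the single Visit 3 sample is taken.

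**The two readings of Figure 2.**

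- Two draws: 8.1 and 11.2 stand. The integrated measure in 1.0, and the AUC in 10.1 read with it, cannot be obtained as described.
- Serial draws: 1.0 and 10.1 can stand, and the count in 8.1 and the volume in 11.2 are wrong.

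The sections disagree under either reading.

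**The case against.** The strongest objection is that section 8.1 leaves draw times to Figure 2, which was not available in the text reviewed. The documents as read therefore cannot show that the trial lacks post-meal samples. If the figure lists serial draws, the outcome is measurable and only a count and a volume need correcting. This stands, and it limits the finding to a conflict between sections. It does not remove the conflict. Sections 8.1 and 11.2 also agree with each other on volume, which makes a single typing slip less likely.

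A second objection is that the reversed group order needs a post-meal Visit 3 sample to be used as the baseline. An incremental area would normally start from a pre-meal value, and nothing in the plan suggests otherwise. Taking Visit 4 as the baseline would restore the order given by the total area. This too is fair. The reversal shows only that section 10.1 leaves the baseline open, and it is not a predicted result. The concentrations and curve in the illustrations are assumed. The conclusion needs only the sample count and the algebra.

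Third, EAA is one of six outcomes and is absent from the hypothesis, which argues for a modest rating. It is still a formally tested outcome that the stated sampling does not support.

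**Conclusion.** The concern holds and should be fixed. As written, 0 or 1 of the 2 plasma samples is post-meal, for 2 meals. A two-point area can be calculated, so section 10.1 alone is not impossible, but that area is not the integrated post-meal response promised in section 1.0.

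Confidence is high that sections 1.0, 8.1, 10.1 and 11.2 must be reconciled with Figure 2. Whether the trial can actually measure the outcome depends on that figure. The algebra assumes a common interval between draws. The two outcomes in the hypothesis are not affected.

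**What to change.** Reconcile sections 1.0, 8.1, 10.1 and 11.2 with Figure 2, by whichever route matches the true schedule.

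- **Two draws are intended.** In 10.1, replace the AUC with plasma EAA concentration at the named Visit 3 and Visit 4 times. Remove the integrated post-meal wording from 1.0 and make no claim about an integrated response. If the Visit 3 draw follows a meal, a claim about concentration at that named time remains open. This adds no procedures, but gives up an outcome that two samples cannot validly measure.
- **Figure 2 already has serial post-meal draws.** Correct the sample count in 8.1 and the blood volume in 8.1 and 11.2. In 10.1, state the AUC window, whether the area is total or incremental and from which baseline, and the calculation method. This adds no procedures, but the risk text on blood volume changes.
- **Figure 2 has two draws and the sponsor wants to keep the AUC.** Extra draws would be needed. How many, and how much blood, depends on a schedule that the documents do not give.

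Under section 12.0, any of these is an amendment that must be submitted to and approved by the IRB.
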